#### Process evaluation data analysis and synthesis

Data at the macro level will be analysed thematically and data analysis at the meso and micro levels will combine thematic and comparative analysis. Synthesis across macro, meso and micro levels will focus on generating in-depth narrative accounts of how the introduction of the intervention has affected the process of shared decision making. We will use the OSIRIS programme theory as the organising device for data synthesis, guiding us to identify the key linkages and mechanisms, ex-post, for implementation of a decision aid for major surgery.

#### 12.9 Follow-up procedures

Investigators will review a participant's medical record and contact participants by telephone to conduct brief interviews at 30 days from surgery for those participants who have undergone surgery and at 180 days after index decision making episode for all patients. To collect data on secondary outcomes and facilitate the health economic analysis, we will request hospital episode statistics and mortality data from NHS Digital (formerly HSCIC) for participants in England or equivalent national database. Prospective consent for ONS/HES (or equivalent national database) data linkage will be sought before enrolment into the trial.

#### 12.10 Minimising bias

It is not possible to conceal treatment allocation from all staff in trials of this type. Patients and staff delivering the intervention will be unblinded. However, by randomising

OSIRIS Protocol v2.0 20.11.2023 Page **23** of **46** 

at the level of hospitals, we will eliminate the possibility of between group/surgeon contamination. All doctors in both groups will experience similar levels of additional observation. It is understood that the standard of shared decision making may improve for all patients regardless of study group allocation due to the raised awareness and scrutiny of trial participation. The trial management group and the trial steering committee will not see results broken down by treatment arm during the trial. Final analysis will occur once all follow up data is collected, the final statistical analysis plan has been signed off and data cleaning has occurred.

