## 7.2 Study setting

The study will take place in the UK across 40 NHS hospitals (approximately 20 hospitals in the intervention arm and 20 hospitals in the usual care arm) and there may be multiple hospitals from single Trust included in the study. Hospitals are the units of randomisation (clusters).

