## 11. Eligibility criteria

#### 11.1 Hospital inclusion criteria

 Provide services for high-risk patients in one or more of the following surgical procedures: elective colorectal bowel resection for cancer, hip-replacement, or abdominal aortic aneurysm surgery

OSIRIS Protocol v2.0 20.11.2023 Page **16** of **46** 

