#### 12.2 Randomisation method

Clusters (hospitals) will be randomised to either intervention or control with a 1:1 allocation ratio. Random permuted blocks randomisation with block sizes of m=4 and 2 will be used. This is a restricted randomisation scheme without stratification. A manual randomisation system (see 12.3) will be used and no adaptive element is envisaged.

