#### 12.6 Intervention

This is a complex intervention, combining training to promote effective shared decision making for high-risk surgical patients (see above) together with a software-based decision support intervention. This software utilises a series of computational models developed by the OSIRIS team, which incorporates modelling of patient outcomes using NHS registry data, and patient-level information on quality of life outcomes after major surgery. Patients and doctors will use the intervention during all decision making encounters with the surgeons and other healthcare staff (e.g. anaesthetists, specialist nurses). By combining data sources from previous studies within this programme of work with NHS registry data the intervention will generate a forecast of important long-term outcomes for the patient. This forecast is presented using a clear and simple user interface with icon arrays and other patient friendly display methods to ensure it is correctly understood. Patients will be able to select and focus on outcomes of most relevance to them, whilst the intervention could highlight important outcomes which the patient might not have considered.

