#### 17.6 Planned sensitivity analysis

There are two planned sensitivity analyses that target the primary estimands.

- 1. Unadjusted analysis accounting for clustering by hospital but no individual participant characteristics including planned surgery
- Model assuming clustering by doctor involved in index decision making episode within hospital

Four sensitivity (secondary) analyses which target different estimands involving the primary outcomes are planned. The estimands for these analyses will be fully specified in the SAP

 An analysis as described in 17.4 using all available data without imputation of outcomes (imputation of co-variates only)

OSIRIS Protocol v2.0 20.11.2023 Page **33** of **46** 

- 2. An analysis as described in 17.4 but excluding all participants whose surgery has been cancelled or delayed by more than 180 days. A principle stratum approach is used for these intercurrent events in which the treatment effect is estimated in the subpopulation of patients in which the event didn't occur. This estimate is unbiased under plausible assumptions [19].
- An analysis as described in 2 but additionally excluding participants who did not initiate their assigned intervention as planned. This is akin to a per-protocol analysis.
- 4. An analysis as described in 17.4 assuming a range of more negative values of DRS and MCS for participants who died within the 180 days follow-up.

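### Section 12.10 claims that randomising hospitals rules out contamination between arms, but hospitals of one Trust can be placed in opposite arms and nothing keeps a trained clinician in one arm

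*Protocol*

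**What the plan says.** Section 12.10 (Minimising bias) accepts that patients and treating staff are unblinded. It then states that, by randomising "at the level of hospitals, we will eliminate the possibility of between group/surgeon contamination". The statement has no qualification.

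The sections that define the clusters read differently:

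- Section 7.2 makes the hospital the unit of randomisation and adds that "there may be multiple hospitals from single Trust included in the study".
- Section 12.2 states: "Clusters (hospitals) will be randomised to either intervention or control with a 1:1 allocation ratio". Permuted blocks of 4 and 2 are used, and "This is a restricted randomisation scheme without stratification". Trust membership plays no part.
- Section 11.1 asks of a hospital only that it "Provide services for high-risk patients in one or more of the following surgical procedures". There is no rule on shared staff and no limit of one hospital per Trust.

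Section 12.6 describes a complex intervention, "combining training to promote effective shared decision making for high-risk surgical patients" with the decision-support software. Section 12.5 describes the training of doctors: workshops, role-play and debriefing. Section 12.7 defines control as local practice without extra training. Sections 14.4 and 14.6 give software access by a personal password that is issued after training.

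**The concern.** The protocol presents freedom from contamination as a consequence of the design, but the design leaves a route open. Two hospitals of one Trust can be allocated to different arms. A surgeon, anaesthetist or pre-operative clinic team working at both would be trained for one and then see control patients at the other. Training in how to hold a shared decision-making consultation cannot be left behind at the intervention site.

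The effect of such carry-over is to shrink the difference between arms. For the DRS superiority test this is conservative. For the MCS it is not: shrinking a true harm makes it easier to conclude that there is none of importance. Section 17.4 declares the intervention effective only if both co-primary results succeed, so the MCS result is the protection against harm to mental health.

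**Working it through.** **1. Is the route open?** One open route is enough to contradict an absolute statement.

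- *Can sister hospitals be split?* Yes. In different blocks the chance of opposite arms is 1/2. Within one block of 4, two of the three other places are in the opposite arm, so it is 2/3. Within one block of 2 it is 1.
- *Does any section tie them together or restrict clinicians?* Not 7.2, 11.1, 12.2, 12.3 or 12.10. Section 14.5 makes non-use of the device at intervention sites a protocol deviation, but no matching rule covers exposure to a trained clinician at control sites. Section 17.3 analyses every cluster as randomised.
- *Does the password close the route?* Only for the software, not for the training.

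**2. The plan's own figures.** Inputs from section 17.1: MCS margin 3.5, SD 11, one-sided 2.5%, power 90%, ICC 0.01, 20% loss; DRS difference 7.5, SD 16.

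- n per arm = 2 × 11² × (1.960 + 1.282)² / 3.5² ≈ 208, so 416 in total.
- With 11.5 analysed per hospital, the design effect is 1 + 10.5 × 0.01 = 1.105, and 416 × 1.105 = 460, as stated.
- 460 / 0.8 = 575, or 14.4 per hospital, rounded up to 15 × 40 = 600.
- DRS power reproduces at 99.8%.

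The sample size is correct and is not in question.

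**3. MCS error under contamination.** With 600 recruited and 20% lost, 480 are analysed, 12 per hospital.

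- Design effect = 1 + 11 × 0.01 = 1.11.
- SE = 11 × √(4 × 1.11 / 480) = 1.058.

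Suppose a fraction c of control patients receives the whole intervention and the true harm equals the margin. The expected observed harm is 3.5(1 − c), and the chance of declaring non-inferiority is 1 − Φ(1.96 − 3.5c / 1.058).

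| c (assumed) | Shift, 3.5c / 1.058 | One-sided error |
|---|---|---|
| 0 | 0 | 2.5% |
| 5% | 0.165 | 3.6% |
| 10% | 0.331 | 5.2% |
| 20% | 0.662 | 9.7% |

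These are upper bounds for each c, because the formula lets the software effect carry over as well. If training carries half of the effect (assumption), c = 10% acts like 5% and the error is about 3.6%.

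As a purely hypothetical yardstick, c = 10% would arise if 4 of 20 control hospitals had half of their trial consultations held by trained clinicians (4/20 × 1/2).

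**4. DRS power under the same dilution.** SE = 16 × √(4 × 1.11 / 480) = 1.539.

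- c = 10%: difference 7.5 × 0.9 = 6.75, power Φ(6.75 / 1.539 − 1.96) = 99.2%.
- c = 20%: difference 6.0, power 97.4%.

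**The case against.** The strongest reply is that the factual core is inferred. The protocol says only that a Trust may contribute more than one hospital. It does not say that any clinician works at two participating hospitals, or that any Trust will have hospitals in both arms. This stands: the text shows that contamination is possible, not that it will occur, and c has no anchor in the documents.

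Second, full transmission is implausible. The software needs a personal password, its users are recorded in the delegation log (section 14.7), and its use is recorded (section 14.5). The mental-health harm that the protocol anticipates comes largely from the technology and its forecast (sections 5 and 7.3), so training alone might not reproduce that harm in control patients. This also stands, and is why the error figures are upper bounds and not estimates.

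Third, section 12.10 acknowledges that decision making may improve in both arms. The cause it names is awareness and scrutiny from trial participation, which is a different route and does not cover shared staff.

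A reader might infer more than the documents support:

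- *That hospitals are allocated independently.* Permuted blocks make allocations dependent. The route remains open all the same.
- *That the trial loses important power on the DRS.* It does not; the consequence there is mainly a diluted estimate.
- *That the doctor-level sensitivity model in section 17.6 ("Model assuming clustering by doctor involved in index decision making episode within hospital") is wrong because it nests doctors in hospitals.* How a doctor seen at two hospitals is coded can be left to the SAP, which is not at hand.

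**Conclusion.** The point holds as a limited one. Section 12.10 claims a property that sections 7.2 and 12.2 do not deliver, and no other section supplies it. Whether contamination occurs depends on whether participating hospitals in opposite arms share clinicians, which the protocol leaves open.

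If it occurs, it biases both co-primary differences towards zero, and on the MCS it favours declaring non-inferiority. The size rests on an assumed c, an unchanged standard error and a true harm equal to the 3.5-point margin. For c between 5% and 20%, the error would be at most 3.6% to 9.7% instead of 2.5%, and less if only training carries over.

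It would be too strong to read this as showing that the error rate is inflated to those levels, or that the arms are in fact contaminated. The documents show neither.

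**What to change.** In sections 7.2 and 12.2, add a check at site set-up, before allocation, of whether participating hospitals share surgical, anaesthetic or pre-operative clinic staff. Hospitals that do should form one cluster with one allocation. Alternatively, require that each clinician sees trial patients in one arm only. Record any clinician who nevertheless works in both arms. In section 12.10, claim that hospital randomisation reduces contamination, not that it removes the possibility.

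The cost is a set-up question, a few sentences and possibly a few clusters fewer. With 36 equal units in place of 40 and 480 analysed:

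- Cluster size = 480 / 36 = 13.3, and design effect = 1 + 12.3 × 0.01 = 1.123.
- SE = 11 × √(4 × 1.123 / 480) = 1.064.
- MCS power = Φ(3.5 / 1.064 − 1.96) = 90.8%, against Φ(3.5 / 1.058 − 1.96) = 91.1% with 40 units.

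Merged clusters would be larger than the rest, so true power would be a little below 90.8%. If the check finds no shared staff, no clusters are lost and the revised sentence in 12.10 has a documented basis.

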#### 12.11 Participant, study and site discontinuation

The right of a participant to refuse participation without giving reasons will be respected. All trial participants are free to withdraw from the trial at any time without giving reasons and without prejudicing their further treatment. They will be provided with a contact point where they may obtain further information about the study. Those participants with a recorded outcome will be included in the final analysis on an intention to treat basis. The withdrawal will be documented in the case report form and medical records. Participants are not obliged to give the reason for withdrawing their consent, but we will attempt to ascertain trends if possible, relating to trial procedures in case this necessitates a protocol amendment.

#### 12.12 End of trial definition

The end of trial is defined as the time point when the last patient last visit has been completed (last 180-day follow-up). The Chief Investigator is delegated the responsibility of submitting the end of trial notification to REC and MHRA once reviewed by the sponsor. The end of trial notification must be received by the REC and MHRA within 90 days of the end of the study. If the study is ended prematurely, the Chief Investigator will notify the Sponsor, REC, and MHRA within 15 days, including the reasons for the premature termination

#### 13. Investigational device

## 13.1 Name and description of Investigational Device

OSIRIS decision aid software is a web-based application hosted on a dedicated secure server. This software has physical components and there will be no physical contact

OSIRIS Protocol v2.0 20.11.2023 Page **24** of **46** 

with humans or bodily fluids. The software has been specifically generated for this study and is described in OSIRIS study Investigator Brochure.

## 14. Legal status of Investigational Device

The OSIRIS Study Software (vx.x, xx.xx.xxx) is not currently authorised for clinical use in the UK and does not have a CE or UKCA mark. There will be one version of the software accessible as a single device by all sites within the study as a secure weblink. The decision aid is a piece of software being used as a standard medical device for use as a decision support tool in shared decision making about surgical treatment. The patient population is high risk patients contemplating elective colorectal bowel resection for cancer, hip replacement or abdominal aortic aneurysm surgery.

The device provides and illustrates medical complications and outcomes of surgery for patient groups with specific comorbidity profiles, based on modelling of historic surgical data from the United Kingdom. The models used have been developed and cross-validated prior to the study and will be fixed during the study with no active learning elements. The device will enable clinicians to illustrate surgical outcomes seen in similar patients rather than using generic population risks when discussion surgical treatment with higher risk patients.

The device will be used in a cluster randomised study (comparator standard surgical consultation). This study is intended to evaluate the acceptability and utility of a personalized decision aid within shared decision making around surgery. The device outcomes forecast is presented as outcomes of similar patients from historic data and this study is not intended nor powered to evaluate these historic risk estimates against actual patient outcomes.

The device is intended and labelled only for use during the OSIRIS trial, and we do not intend to commercial this version of the device beyond this study.

#### 14.1 Device manufacturer and supply arrangements

This device has been manufactured in house with Queen Mary University of London it is not intended for commercialisation. Only one 'device' will be maintained and used for the proposed study. QMUL will take on all responsibilities of a manufacturer for the purposes of the proposed trial only. As a centralised piece of software there are no shipping, distribution or recall arrangements.

OSIRIS Protocol v2.0 20.11.2023 Page **25** of **46** 

#### 14.2 Investigational device software

This device is one central piece of software. There will be no local installation or configuration. The software will be accessed through a secure weblink and will be used only on the following browsers: Google Chrome, Apple Safari, Mozilla Firefox, Microsoft Edge, iOS Safari on iPhone/ iPad and Android Google Chrome.

# 14.3 Packaging and labelling of investigational device

As a stand-alone software there is no packaging required. The device is labeled as an investigational medical device exclusively for use within the OSIRIS trial following ISO14155 GCP. Users will be required to acknowledge this label text prior to use.

## 14.4 Accountability and traceability

One version of the device will be maintained on a central server by the software development team. Access to the software will be via personalized password for each local team member.

#### 14.5 Assessment of compliance

The device will be used only by trained investigators during the clinical study, Use of the device will be recorded within the study documentation, non-use of the device for consented patients in intervention sites will be recorded as a protocol deviation.

#### 14.6 Device training and experience requirements

A training package for the use of the device within a shared decision-making encounter has been developed and is documented in the Investigator Brochure (vx.x, xx.xx.xxx). Training will be provided by the central study team and recorded in the site delegation log. Training will be required for issuing of a password to access the device online.

#### 14.7 Administration of investigational device

The device will be used by surgeons, anaesthetists and nurses participating in the clinical trial and recorded in the site delegation log. It will be used during clinical consultation with patients regarding proposed surgery.

OSIRIS Protocol v2.0 20.11.2023 Page **26** of **46** 

#### 14.8 Destruction, return and recall devices

One device will be maintained centrally during the study and will be taken offline upon completion of the study.

## 14.9 Usage modifications and delays

Use of the device will only be by a clinician who routinely assesses and counsels patients around the risks of surgery and participates in shared decision making. All device outputs will be reviewed considering this experience. Should the device by unavailable or fail due to internet disruption local network failure or other reasons the clinician will revert to existing standard of care practice in providing information regarding surgical risk and shared decision making.

#### 14.10 Management of device specific adverse events

In the event of device failure clinician will revert to standard of care provision of information and shared decision making according to their usual practice outside of the clinical trial and documented as a protocol deviation. All device outputs will be reviewed by experienced clinicians for consistency with the patient's background and characteristics.

#### 14.11 Management of incorrect usage

All users will be experienced clinicians who have undergone study specific training. A risk analysis is provided within the study software documentation.

The following controls will be used:

- a. software replaces no existing essential function
- b. all outputs from the decision aid will be reviewed by experienced clinician for consistency prior to use. The device will not be used directly by patients.
- c. Labelling of device will limit use to the study only. Label text will need to be acknowledged by used. Access to device only by password to trained users in study team.
- d. Skilled clinician will elicit patient worries and preferences prior to using software and will be able to recognise any distress and contextualise risk.

OSIRIS Protocol v2.0 20.11.2023 Page **27** of **46** 

# 15. Safety reporting

#### 15.1 General definitions

Term	Definition				
Adverse Event (AE)	Untoward medical occurrence, unintended disease or injury, or untoward				
	clinical signs (including abnormal laboratory findings) in subjects, users or				
	other persons, whether or not related to the investigational medical device				
	and whether anticipated or unanticipated.				
Adverse Device Event	Adverse event related to the use of an investigational medical device.				
(ADE)					
Device Deficiency	Inadequacy of a medical device with respect to its identity, quality, durability,				
	reliability, usability, safety or performance.				
Serious Adverse Event	Adverse event that led to any of the following:				
(SAE)	a) death				
	b) serious deterioration in the health of the subject, users, or other				
	persons as defined by one or more of the following:				
	a. a life-threatening illness or injury, or				
	b. a permanent impairment of a body structure or a body				
	function including chronic disease, or				
	c. in-patient or prolonged hospitalisation				
	d. medical or surgical intervention to prevent life-threatening				
	illness or injury, or permanent impairment to a body				
	structure or a body function				
	c) foetal distress, foetal death, a congenital abnormality, or a birth				
	defect including physical or mental impairment.				
Serious Adverse	Adverse device effect that has resulted in any of the consequences				
Device Effect	characteristic of a serious adverse event.				
Unanticipated serious	Serious adverse device effect which by its nature, incidence, severity, or				
adverse device effect	outcome has not been identified in the current risk assessment.				
(USADE)					

